4.2.1.2. Objective Response Rate, and Disease Control Rate

Objective response rate (ORR) by RECIST will be calculated using two different ways:

- Scenario #1: ORR will be calculated using a strict interpretation of RECIST Version 1.1. Objective response will be derived as no/yes variable. Patients with a BOR of confirmed CR or PR will be assigned ‘Yes’. Patients not having a BOR of confirmed CR or PR will be assigned ‘No’. Hence, ORR is defined as the proportion of patients with confirmed objective response being “Yes”.
- Scenario #2: ORR_{UNCONFIRMED} will be calculated using all responses regardless of confirmation. Objective response will be derived as no/yes variable. Patients with a BOR of confirmed CR, confirmed PR, unconfirmed CR or unconfirmed PR will be assigned “Yes”. All patients with other BOR values will be assigned “No”. Hence, ORR_{UNCONFIRMED} is defined as the proportion of patients with unconfirmed objective response being “Yes”.

Both ways (confirmed and unconfirmed) of assigning BOR will be implemented.

ORR defined as the proportion of patients with a confirmed BOR of complete response (CR) or partial response (PR) as determined by the investigator using RECIST v1.1.

ORR by RANO is defined as the proportion of patients with a BOR of complete response (CR) or partial response (PR) or MR as determined by the investigator using RANO.

Disease control rate (DCR) by RECIST is defined as the proportion of patients with a BOR of CR, PR, or SD lasting at least 7 weeks as determined by the investigator using RECIST v1.1.

DCR by RANO is defined as the proportion of patients with a BOR of CR, PR, MR, or SD lasting at least 7 weeks as determined by the investigator using RANO criteria for glioma patients.

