9.2.7 Efficacy Analysis

The investigator shall evaluate efficacy according to the corresponding criteria for all subjects according to RECIST Version 1.1 (RANO criteria for glioma subjects).

Efficacy evaluation indicators include ORR, DCR, DoR, TTR, PFS, and OS.

- ORR: Defined as the proportion of subjects achieving a best overall response of confirmed complete response (CR) or partial response (PR)
- DCR: Defined as the proportion of subjects achieving a best overall response of confirmed CR, PR, or stable disease (SD)
- DoR: Defined as the time from the first occurrence of PR or CR, whichever comes first until disease progression or death
- TTR: Defined as the time from the start of study treatment to the first occurrence of objective response (PR or CR, whichever comes first)
- PFS: Defined as the time (months) from the start of study treatment until the first radiographic documentation of objective progression as assessed by the investigator using RECIST Version 1.1 or death from any cause
- OS: Defined as the time from the start of the study drug until death from any cause

The estimate of ORR and DCR and the corresponding 95% CI will be presented by tumor type. For time-to-event endpoints such as PFS, TTR, DoR, and OS, the medians and rates at various time points along with 95% CI will be estimated by Kaplan-Meier methodology.

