4.2.1.3. Duration of Response

Duration (months) of response (DoR) by RECIST is defined as the time from the first occurrence

of confirmed PR or confirmed CR by RECIST v1.1, until disease progression or death, whichever comes first. Only those patients with objective responses of confirmed CR or confirmed PR will be included in this analysis.

DoR by RANO is defined as the time from the first occurrence of CR or PR or MR by RANO, until disease progression or death, whichever comes first. Only those patients with objective responses of CR or PR will be included in this analysis.

The DoR is calculated as (date of death or PD or last assessment – date of first occurrence of CR or PR or MR + 1)/30.4375. Censoring will follow the rules outlined for PFS in [Table 3](#).

Table 3 Outcome and Event or Censoring Dates for Duration of Response

Rule	Situation	Date of Event or Censoring	Outcome
1	PD documented from schedule tumor assessment visits	Date of first documented PD	Event
2	Death without PD or death after one missing tumor assessment visit	Date of death	Event
4	No death or PD by the time of data cut-off for analysis	Date of last adequate tumor assessment prior to or on analysis data cutoff date	Censored
5	Early discontinuation (lost to follow-up or withdrawal of consent) of study without death or PD	Date of last adequate tumor assessment	Censored
6	New anti-tumor therapy started prior to PD	Date of last adequate assessment prior to or on date of initiation of new therapy visit	Censored
7	Death or PD after two or more consecutive missed or inadequate tumor assessment visits	Date of last adequate tumor assessment prior to missed visits	Censored

Note: An adequate radiologic assessment is defined as an assessment where the Investigator determined radiological response is CR, PR, SD, or PD. If PD and new anti-cancer medication occur on the same day, will assume that the progression was documented first, e.g. outcome is progression and the date is the date of the assessment of progression

Determination of two or more consecutive missing or inadequate assessments

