4.2.1.4. Time-to-response

Time (months) to response (TTR) by RECIST is defined as the time from start of study treatment until the date of first documented objective response, either confirmed CR or confirmed PR (whichever status is recorded first), according to RECIST v1.1. It will be calculated for patients whose BOR is either confirmed CR or confirmed PR.

TTR by RANO is defined as the time from start of study treatment until the date of first documented objective response, either CR or PR or MR (whichever status is recorded first), according to RANO. It will be calculated for patients whose BOR is either CR or PR or MR.

TTR is calculated as (date of first occurrence of CR or PR or MR – date of start of study treatment + 1)/30.4375.

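### For glioma, the SAP's RANO duration of response starts at a minor response but leaves out patients whose best response is minor, although ORR and TTR count them as responders

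*SAP*

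**What the plan says.** **SAP, RANO endpoints for glioma**

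- ORR (4.2.1.2): "ORR by RANO is defined as the proportion of patients with a BOR of complete response (CR) or partial response (PR) or MR".
- TTR (4.2.1.4): the time to the first CR, PR or MR. "It will be calculated for patients whose BOR is either CR or PR or MR".
- DoR (4.2.1.3), start: "DoR by RANO is defined as the time from the first occurrence of CR or PR or MR by RANO". The calculation line in the same section repeats the MR start.
- DoR (4.2.1.3), who is included: "Only those patients with objective responses of CR or PR will be included in this analysis".
- Best overall response (4.2.1.1): one MR scan is enough for MR. A PR that fails the PR rule is downgraded to MR.

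**Protocol Amendment 2, section 9.2.7**

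Efficacy is evaluated "according to RECIST Version 1.1 (RANO criteria for glioma subjects"), and one set of definitions then serves both criteria.

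- ORR: "Defined as the proportion of subjects achieving a best overall response of confirmed complete response (CR) or partial response (PR").
- DoR: "Defined as the time from the first occurrence of PR or CR, whichever comes first until disease progression or death".
- TTR: runs to "the first occurrence of objective response (PR or CR, whichever comes first").

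MR appears in none of these. Appendix 9 lists it as a category of its own, below partial response.

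**Change log and version**

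SAP Section 7 lists three changes from the protocol, and none concerns MR, ORR, DoR or TTR. SAP Section 1 says that the SAP is based on Protocol Amendment 3. The protocol supplied is Amendment 2.

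**The concern.** DoR is read as the duration of the responses counted in ORR. Here the two do not match. The DoR start date treats MR as a response, while the inclusion sentence does not. Two programmers could each defend a different table from the same section.

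Two things are at stake. The reported glioma DoR would describe only some of the patients reported as responders. For those patients it would also include time before they reached the CR or PR that admitted them. Separately, the glioma ORR could exceed the rate defined in Amendment 2 without the change being declared.

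**Working it through.** The documents give no figure for this point, so there is nothing to reproduce. The check compares the definitions and then applies them to example scan sequences.

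**1. Definitions side by side (RANO)**

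| Endpoint | Responders, SAP | Clock, SAP | Amendment 2, 9.2.7 |
|---|---|---|---|
| ORR | CR, PR, MR | not applicable | confirmed CR or PR |
| TTR | CR, PR, MR | ends at first CR/PR/MR | ends at first PR/CR |
| DoR | CR, PR | starts at first CR/PR/MR | starts at first PR/CR |

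Within the SAP, ORR and TTR agree. DoR is the outlier: its start date matches them and its population does not.

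**2. Inputs and formulas**

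Scans fall on study days 57, 113, 169 and 253: every 8 weeks to week 24 and then 12 weeks later, as in Protocol 6.1.13. The SAP formulas are:

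- TTR = (date of first response − first dose + 1)/30.4375, which is study day/30.4375.
- DoR = (date of PD − date of first response + 1)/30.4375.

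The DoR inclusion sentence is read as referring to best overall response.

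**3. Patient (a): MR, PR, PR, PD**

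The two PRs are 169 − 113 = 56 days apart, so best response is PR and the patient enters all three analyses.

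- DoR from MR, as the SAP is written: (253 − 57 + 1)/30.4375 = 197/30.4375 = 6.47 months.
- DoR from first PR: (253 − 113 + 1)/30.4375 = 141/30.4375 = 4.63 months.
- Difference: 56/30.4375 = 1.84 months.
- TTR: 57/30.4375 = 1.87 months to MR, against 113/30.4375 = 3.71 months to PR.

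**4. Patient (b): MR, SD, PD (days 57, 113, 169)**

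Best response is MR. The patient is in ORR and TTR but not in DoR. From the MR, the duration would be (169 − 57 + 1)/30.4375 = 113/30.4375 = 3.71 months.

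**5. Patient (c): SD, PR, PD (days 57, 113, 169)**

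The PR is downgraded to MR. The patient is in ORR and TTR but not in DoR. The duration would be (169 − 113 + 1)/30.4375 = 57/30.4375 = 1.87 months.

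**6. The three patients together**

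- SAP as written: three responders in ORR and TTR, one patient in DoR, with 6.47 months.
- One CR/PR set, confirmed: one responder, DoR 4.63 months.
- One CR/PR/MR set: three responders, DoR 6.47, 3.71 and 1.87 months, median 3.71.

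In this example the DoR as written is longer than under either consistent rule.

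**7. Size for ORR (assumed counts)**

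The number of glioma patients is not given. Suppose 10% have CR/PR and a further 20% have MR only. Clopper-Pearson 95% intervals:

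| Glioma patients | CR/PR | CR/PR/MR |
|---|---|---|
| 10 | 1 (10%; 0.3–44.5) | 3 (30%; 6.7–65.2) |
| 20 | 2 (10%; 1.2–31.7) | 6 (30%; 11.9–54.3) |
| 30 | 3 (10%; 2.1–26.5) | 9 (30%; 14.7–49.4) |

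In each row DoR would rest only on the CR/PR patients: 1, 2 or 3.

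**The case against.** The strongest reply is that this is a drafting slip. The DoR definition and its calculation line both include MR, and SAP 4.2.1.2 makes MR an objective response, so adding MR to the inclusion sentence would restore consistency. That may well be the intent. But the sentence as it stands is an explicit rule, and following it gives the results above.

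Other points on that side also carry weight:

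- **Visibility.** SAP 4.2.1.1 and 5.2.9.1 tabulate best response with MR separate, so a reader can derive a CR+PR rate. That rate follows the SAP's RANO rules, under which one CR scan suffices, so it need not equal the confirmed rate of Amendment 2. The DoR mismatch cannot be undone from that table.
- **Choice of endpoint.** Counting MR may be reasonable in low-grade glioma. The issue is consistency and disclosure.
- **Consequence.** Only dose escalation is analysed, no hypothesis test is planned, and the RP2D criteria in Protocol 4.1.1 are MTD, safety, PK and PD.

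A reader might also infer more than the documents support:

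- **That ORR, TTR and DoR use three different responder sets.** They do not. RANO ORR and TTR share one set.
- **That by-dose ORR pools RECIST responses with RANO minor responses.** SAP 5.1.1 presents efficacy by dose level and by disease type, while Table 11 lists dose groups only. Pooling is one reading of that wording.
- **That MR must be confirmed after at least four weeks.** Protocol Appendix 9 asks for a sustained decrease only for PR. Any estimate of false MRs from measurement noise would need an error SD that the documents do not give.

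**Conclusion.** The contradiction inside SAP 4.2.1.3 is certain and does not depend on the protocol version. RANO DoR omits MR-only responders who count in ORR and TTR, and it adds earlier MR time to the DoR of CR/PR patients. With MR one 8-week scan before PR, the addition is 1.84 months (6.47 against 4.63). The effect on the reported median depends on how many glioma patients have MR only, or MR before PR, and neither number is known.

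The departure from the protocol is established only against Amendment 2. Amendment 3 could already count MR. The two versions may well differ: SAP Section 7 mentions a DLT-equivalent summary defined in the protocol, and I find none in Amendment 2. It would therefore go too far to say that the SAP breaks the protocol on which it is based. It would also go too far to say that the glioma ORR is inflated. It could be higher than the Amendment 2 rate, and the two coincide if every SAP responder also has a confirmed CR or PR.

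These are secondary, descriptive endpoints, so no type I error or power is affected. The rule should still be corrected, because as written it gives a DoR that does not belong to the reported ORR.

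**What to change.** Use one responder set and one start date within each RANO analysis.

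1. Report glioma ORR as CR+PR, the Amendment 2 endpoint, and state how its confirmation requirement applies. Give DoR and TTR from the first CR or PR in those patients.
2. Beside it, report a labelled CR+PR+MR rate. Give DoR and TTR from the first CR, PR or MR in all of those patients, including MR-only.
3. Add MR to the definition of an adequate assessment under SAP Tables 3 and 5, which names only CR, PR, SD and PD. MR scans will otherwise not count when DoR is censored.
4. State that RECIST and RANO ORR are not combined in by-dose summaries.
5. Check Amendment 3. If it does not already count MR, list the change in SAP Section 7.

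No new data are needed. The cost is SAP wording, a few extra table rows and a possibly lower headline glioma ORR.

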4.2.1.3. Duration of Response

Duration (months) of response (DoR) by RECIST is defined as the time from the first occurrence

of confirmed PR or confirmed CR by RECIST v1.1, until disease progression or death, whichever comes first. Only those patients with objective responses of confirmed CR or confirmed PR will be included in this analysis.

DoR by RANO is defined as the time from the first occurrence of CR or PR or MR by RANO, until disease progression or death, whichever comes first. Only those patients with objective responses of CR or PR will be included in this analysis.

The DoR is calculated as (date of death or PD or last assessment – date of first occurrence of CR or PR or MR + 1)/30.4375. Censoring will follow the rules outlined for PFS in [Table 3](#).

Table 3 Outcome and Event or Censoring Dates for Duration of Response

Rule	Situation	Date of Event or Censoring	Outcome
1	PD documented from schedule tumor assessment visits	Date of first documented PD	Event
2	Death without PD or death after one missing tumor assessment visit	Date of death	Event
4	No death or PD by the time of data cut-off for analysis	Date of last adequate tumor assessment prior to or on analysis data cutoff date	Censored
5	Early discontinuation (lost to follow-up or withdrawal of consent) of study without death or PD	Date of last adequate tumor assessment	Censored
6	New anti-tumor therapy started prior to PD	Date of last adequate assessment prior to or on date of initiation of new therapy visit	Censored
7	Death or PD after two or more consecutive missed or inadequate tumor assessment visits	Date of last adequate tumor assessment prior to missed visits	Censored

Note: An adequate radiologic assessment is defined as an assessment where the Investigator determined radiological response is CR, PR, SD, or PD. If PD and new anti-cancer medication occur on the same day, will assume that the progression was documented first, e.g. outcome is progression and the date is the date of the assessment of progression

Determination of two or more consecutive missing or inadequate assessments

In the derivation of duration of response, if a patient has a tumor assessment after two or more consecutive missed or inadequate tumor assessments, the patient will be censored at the last adequate tumor assessment. The following provides the rules for determining whether two or more consecutive tumor assessments are missed, of note, the relative day in the rules refers to the first dose date of study drug.

- If the tumor assessment date is prior to day 1 of week 17 (relative day $< (16 + 1) \times 7 + 1 = 120$), and the difference between the tumor assessment date and the next adjacent adequate tumor assessment ≥ 126 days ($= 2 \times (8 \text{ weeks} \times 7 + 7)$), then the tumor assessment is considered as occurring after two or more consecutive missing tumor assessments;

- If the tumor assessment date is between day 1 of week 17 and day 1 of week 25 (relative day between $(16 + 1) \times 7 + 1 = 120$ and $(24 + 1) \times 7 + 1 = 176$), and the difference between the tumor assessment date and the next adjacent adequate tumor assessment ≥ 161 days ($= (8 \text{ weeks} * 7 + 7 + 12 \text{ weeks} * 7 + 2 \text{ weeks} * 7)$), then the tumor assessment is considered as occurring after two or more consecutive missing tumor assessments;
- If the tumor assessment date is on or after day 1 of week 25 (relative day $\geq (24 + 1) \times 7 + 1 = 176$), and the difference between the tumor assessment date and the next adjacent adequate tumor assessment ≥ 196 days ($= 2 * (12 \text{ weeks} * 7 + 2 \text{ weeks} * 7)$), then the tumor assessment is considered as occurring after two or more consecutive missing tumor assessments.

Reasons for censoring are included in [Table 4](#) following the hierarchy.

Table 4 Duration of Response Censoring Reasons and Hierarchy

Hierarchy	Condition	Censoring Reason
1	New anti-tumor therapy started prior to PD	New anti-tumor therapy started prior to PD
2	Two or more consecutive missed or inadequate radiological assessment visits	Two or more consecutive missed or inadequate radiological assessment visits
3	Drops out before end of study, no PD or death, lost to follow-up	No death nor PD, lost to follow-up
4	Drops out before end of study no PD or death, withdrawal by subject from the study	No death nor PD, withdrawal by subject
5	No death nor PD by the time of data cut-off for the analysis	No death nor PD by the time of data cut-off for the analysis

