4.2.1.5. Progression-free Survival

PFS is defined as the time (months) from the date of first administration of study treatment until the first radiographic documentation of objective progression as assessed by investigator using RECIST v1.1 or RANO criteria for glioma patients, or death from any cause.

More specifically, PFS will be determined using all the assessment data up until the last evaluable

visit prior to or on the date of

- (i) disease progression as defined by RECIST Version 1.1 or RANO or death; or
- (ii) withdrawal of consent or lost to follow-up; or
- (iii) receiving subsequent anti-cancer medication, whichever is earlier.

Patients without report of PD or death from any cause at the time of analysis are censored as described in [Table 5](#) below.

The PFS time will always be derived based on scan dates not tumor assessment dates. RECIST or RANO assessments/scans contributing towards a particular visit may be performed on different dates. The following rules are applied:

- Date of progression is determined based on the earliest of the dates of the component that triggered the progression.
- When censoring a patient for PFS, the patient is censored at the latest of the dates contributing to a particular overall visit assessment.

Table 5 Outcome and Event or Censoring Dates for PFS

Rule	Situation	Date of Progression or Censoring	Outcome
1	PD documented from radiological assessment visits	Date of first documented disease progression	Event
2	Death without PD or death after one missing radiological assessment visit	Date of death	Event
3	No baseline nor post-baseline radiological assessments available	Date of first administration of study treatment	Censored
4	No death or PD by the time of data cut-off for analysis	Date of last adequate radiological assessment	Censored
5	Early discontinuation (lost to follow-up or withdrawal of consent) of study without death or PD	Date of last adequate radiological assessment	Censored
6	New anti-tumor therapy started prior to PD	Date of last adequate radiological assessment prior to or on date of initiation of new therapy visit	Censored
7	Death or PD after two or more consecutive missed or inadequate radiological assessment visits	Date of last adequate radiological assessment prior to missed visits	Censored

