Note: An adequate radiologic assessment is defined as an assessment where the Investigator determined radiological response is CR, PR, SD, or PD. If PD and new anti-cancer medication occur on the same day, will assume that the progression was documented first, e.g. outcome is progression and the date is the date of the assessment of progression

Note: The same algorithm for determination of two or more consecutive missing or inadequate assessments can be found in [Section 4.2.1.3](#).

PFS is calculated as (date of progression or censoring as per rules in [Table 5](#) – date of first administration of study treatment + 1)/30.4375. Reasons for censoring are included in [Table 6](#) following the hierarchy.

Table 6 PFS Censoring Reasons and Hierarchy

Hierarchy	Condition	Censoring Reason
1	No baseline nor post-baseline tumor assessments available	No baseline nor post-baseline tumor assessments
2	New anti-tumor therapy started prior to PD	New anti-tumor therapy started prior to PD
4	Two or more consecutive missed or inadequate radiological assessment visits	Two or more consecutive missed or inadequate radiological assessment visits
5	Drops out before end of study, no progression or death, lost to follow-up	No death nor PD, lost to follow-up
6	Drops out before end of study no progression or death, withdrawal by subject from the study	No death nor PD, withdrawal by subject
7	No death nor PD by the time of data cut-off for the analysis	No death nor PD by the time of data cut-off for the analysis

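### SAP 4.2.1.3 states two conflicting missed-scan censoring rules for duration of response, and its gap test cannot classify a death with no later scan

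*SAP*

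**What the plan says.** **Narrative rule, DoR.** Under the SAP 4.2.1.3 subheading on determining consecutive missing assessments, the text says "if a patient has a tumor assessment after two or more consecutive missed or inadequate tumor assessments, the patient will be censored". The date it gives is the last adequate assessment: "the patient will be censored at the last adequate tumor assessment". Neither death nor PD is required, and the date is not tied to the gap.

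**Outcome table, DoR.** Table 3 rule 7 is limited to "Death or PD after two or more consecutive missed or inadequate tumor assessment visits", with the date "Date of last adequate tumor assessment prior to missed visits". Rule 1 counts documented PD as an event. Rule 2 counts a death without PD, or after one missed visit, as an event. Rule 4 handles patients with neither, and its date is "Date of last adequate tumor assessment prior to or on analysis data cutoff date".

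**Outcome table, PFS.** Table 5 rule 7 (SAP 4.2.1.5) is likewise limited to "Death or PD after two or more consecutive missed or inadequate radiological assessment visits". A note adds: "The same algorithm for determination of two or more consecutive missing or inadequate assessments can be found in" section 4.2.1.3.

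**Reason tables.** Table 4 lists the condition simply as "Two or more consecutive missed or inadequate radiological assessment visits", ranked above the reason for patients with no death or PD by cut-off. Table 6 does the same for PFS.

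**Gap test.** The three bullets compare an assessment date with the next adequate assessment, using thresholds of 126, 161 and 196 days.

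**The concern.** A missed-scan rule exists because a PD or death found after a long unobserved interval has an uncertain event time. That reason disappears once the patient returns with an adequate scan showing no progression: the interval is then known to be progression-free, and a later PD is as well dated as any other. The narrative sentence makes no such distinction. Programmed literally, it would drop valid follow-up or turn a well-documented PD into a censored observation, while Table 3 treats the same patient differently. Two programmers could derive different DoR values from the same section.

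The gap test has its own hole. Rules 2 and 7 in both outcome tables require deaths to be sorted into those after one missed visit (event) and those after two or more (censored). The bullets offer no way to do this when no scan follows.

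**Working it through.** **Step 1. Reproduce the SAP's own figures.** Cut-points: (16+1)×7+1 = 120 and (24+1)×7+1 = 176. Thresholds: 2×(8×7+7) = 126; 8×7+7+12×7+14 = 161; 2×(12×7+14) = 196. All five agree with the SAP.

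**Step 2. Scan days.** Protocol 6.1.13 schedules scans every 8 weeks to week 24 and every 12 weeks thereafter. With day 1 as first dose, the nominal days are 57, 113, 169, 253, 337, 421 and 505.

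**Step 3. Illustrative RECIST patient (scan results assumed).** PR on days 57 and 113; days 169 and 253 missed; PR on day 337; PD on day 421. The first two PRs are 56 days apart, above the 4-week minimum in SAP Table 2, so the response is confirmed before the gap.

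- Gap 337 − 113 = 224 days. The threshold is 126 if chosen by the earlier scan and 196 if chosen by the later one; it is flagged either way.
- Scan before PD: 421 − 337 = 84 days, below 196, so not flagged.

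**Step 4. DoR**, by the SAP formula (end − first response + 1)/30.4375:

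| Reading | Calculation | Result |
|---|---|---|
| Narrative trigger, rule 7's pre-gap date | (113 − 57 + 1)/30.4375 | 1.87 months, censored |
| Narrative trigger, latest adequate scan before PD | (337 − 57 + 1)/30.4375 | 9.23 months, censored |
| Narrative trigger, latest adequate scan, PD scan included | (421 − 57 + 1)/30.4375 | 11.99 months, censored |
| Table 3, rule 7 limited to the gap immediately before the event | (421 − 57 + 1)/30.4375 | 11.99 months, event |

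Under each narrative reading the PD is lost as an event; the first also discards 421 − 113 = 308 days. If instead there is no PD and adequate scans run to day 505, the pre-gap date gives 1.87 months and rule 4 gives (505 − 57 + 1)/30.4375 = 14.75 months, both censored. If the day 337 scan were itself PD, the narrative with the pre-gap date and rule 7 would both censor at day 113. With that date, the rules differ only when the first scan after the gap is not PD.

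**Step 5. PFS, only if the narrative trigger is carried over or rule 7 is taken to cover any earlier gap.** (113 − 1 + 1)/30.4375 = 3.71 months, censored, against (421 − 1 + 1)/30.4375 = 13.83 months, event. The patient would leave the risk set before the 6-, 9- and 12-month landmarks in SAP 5.2.9.1 although progression-free at each.

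**Step 6. Death without a later scan.** Suppose the last adequate scan is SD on day 57 and the patient dies unscanned. There is no next assessment, so the bullets return no answer. Rule 2 would make the death an event; rule 7 would censor PFS at (57 − 1 + 1)/30.4375 = 1.87 months. Measuring to the death date settles it: a death before day 57 + 126 = 183 is an event, and one from day 183 on is censored.

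**The case against.** The best reply is that the SAP names its governing rules. Section 4.2.1.3 sends DoR censoring to Table 3, and section 4.2.1.5 calculates PFS from dates set by Table 5. The disputed sentence only introduces a gap-detection algorithm, so a sensible programmer would follow the tables. Much of this stands, and it rules out three stronger readings that a reader might infer:

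- *That the SAP as written censors PFS at the pre-gap scan for every returning patient.* The sentence concerns DoR, and the note to Table 5 imports only the algorithm.
- *That the sentence itself dictates the pre-gap date.* That qualification appears only in rule 7.
- *That Tables 4 and 6 are independent censoring triggers.* They give no date or outcome. They assign reasons to censored patients, and their wording could mislabel a reason.

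The reply does not remove the DoR conflict. The sentence is a censoring instruction, not merely a definition of a gap, and nothing says which text prevails where it departs from Table 3. Nor is rule 7 airtight: it speaks of PD or death after missed visits, not immediately after. A PD that follows resumed scanning is literally after an earlier gap, while rule 1 calls it an event. The reply also leaves the death problem untouched.

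On consequence, it is fair to add that listings and the swimmer plot keep individual histories visible, and that the RP2D criteria in protocol 4.1.1 are the MTD, safety, PK and PD (pharmacodynamics).

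**Conclusion.** The point holds as an internal contradiction in the DoR rules plus an incomplete gap test for deaths in both DoR and PFS. For the illustrative responder the choice is between 1.87 months censored and 11.99 months with an event. The scan results are assumed, the first figure needs rule 7's date joined to the narrative's trigger, and the second needs rule 7 read as the gap immediately before the event. The PFS contrast of 3.71 against 13.83 months is conditional, as set out in Step 5.

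Severity is modest. The endpoints are secondary and descriptive, with no hypothesis test (SAP 5.2.9). A reader might infer that a definite share of patients is affected; neither document gives a rate of missed scans, so none can be stated. Still, Part 1 expects about 27 to 36 patients (SAP 2.3.1), efficacy is displayed by dose level and disease type (SAP 5.1.1), and DoR uses responders only, so one misclassified patient could move a reported median.

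The thresholds are taken as given here; whether they are well placed is a separate question.

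**What to change.** Replace the narrative sentence in SAP 4.2.1.3 with:

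> If PD or death occurs and the interval from the last adequate assessment before it to the PD or death date meets the threshold below, the patient is censored at that assessment; a gap followed by an adequate non-PD assessment does not cause censoring.

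Reword the bullets to measure that same interval, so that deaths without a later scan are covered. State that rule 7 in Tables 3 and 5 means PD or death immediately after the gap. In Tables 4 and 6, add *followed by PD or death* to the missed-visit condition.

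The cost is SAP wording and a matching check of the derivation programs before database lock. No new data are needed. If the lock has passed, SAP section 1 already provides for recording departures from the plan in the clinical study report, and the rule actually programmed should be stated there.
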